3. Knee Injury and Osteoarthritis Outcome Score (KOOS) self-report survey Pain subscale score > 53.1 and Symptom subscale score > 44.9
4. Cleared by physician to resume physical activity, and currently physical active at least 20 minutes 3x per week
5. Quadriceps central activation ratio < 95%

Exclusion Criteria

6. History of ACL graft rupture
7. History of neurological disorder
8. History of musculoskeletal injury to either leg within the 6 months prior to participation
9. Pregnant or planning to become pregnant

---

Number Of Subjects	75
Study Duration	Each subject's participation will last approximately 3 hours and 45 minutes over approximately 2 weeks.  The entire study is expected to last 3 years.
Study Phases	(1) Screening : screening for eligibility and obtaining consent and (2) Intervention : study intervention/experimental treatment. Phase 2 will involve 2 testing sessions separated by approximately 1 week.
Screening	
Study Treatment	
Follow-Up	
Efficacy Evaluations	
 
1. Gait biomechanics (vertical ground reaction force linear and instantaneous loading rates, peak internal knee extension moment, peak internal knee valgus moment)
 
2. Somatosensory function (knee joint position sense error)
 
3. Quadriceps function (isometric peak torque)
 

Statistical And Analytic Plan	Pre-Post change scores for each of the primary outcomes will be compared between groups via one-way ANCOVA
DATA AND SAFETY MONITORING PLAN	[name] from the UNC-Chapel Hill Department of Orthopaedics will serve as the Research Monitor for this investigation. The PI will provide the Research Monitor a summary report during each quarter of the funding period that details information detailing enrollment, verification of informed consent, and adverse event documentation. The Research Monitor's primary responsibilities relate to the proper conduct of the investigation and the welfare of the subjects who are involved. As such, [name] will have the authority to suspend research associated with the project in the event of violations of study protocol.

---

[figure not shown]

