### **3.2 Allocation to Treatment Groups and Blinding (if applicable)**

Stratified randomization into 3 groups of equal size (n = 25) will be performed using a computer generated randomization algorithm. This algorithm will ensure stratification with respect to age and time since ACLR.

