### **6.2 Statistical Methods**

**Specific Aim 1: To determine the effects of WBV and LMV on quadriceps function, proprioception, and gait biomechanics in individuals with ACLR.**

Analyses for Aim 1 will be performed using pre-post change scores for quadriceps function, proprioception, and gait biomechanics as dependent variables in separate statistical models. Mean change scores will be compared across groups (WBV, LMV, and Control) via one-way analysis of covariance (ANCOVA). Dunnett's procedure will be used to evaluate each the least-squares means for each of the intervention arms (WBV and LMV) versus control in a relatively powerful manner while controlling the overall significance level at two-sided 0.05. The corresponding pre-test values for each dependent variable will be managed as a covariate in these models to increase precision of the treatment effects, as well as to account any random imbalances among the groups with respect to these pre-scores. Other covariates would include variables with random imbalances across the groups measured at the pre-test.

The number of individuals who display HST prior to and following the intervention (or control) will be compared via McNemar's test. This analysis produces a  $\chi^2$  statistic for paired samples (i.e., the proportion with HST at pre-test vs. post-test, separately for each group).

**Specific Aim 2: To compare the effects of WBV and LMV on quadriceps function, proprioception, and gait biomechanics in individuals with ACLR.**

Aim 2 will be evaluated using the statistical models described above for Aim 1, but with focus on the statistical contrast of WBV versus LMV. Specifically, the pre-post change scores for each dependent

variable, adjusted for covariates, will be tested for the pairwise comparison of WBV versus LMV at the two-sided 0.05 significance level.

**Specific Aim 3: To identify factors that predict the effects of LMV and WBV on quadriceps function, proprioception, and gait biomechanics in individuals with ACLR.**

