Aim 3 will be evaluated using multiple regression models. Pre-post change scores for each dependent variable will be included only for the WBV and LMV groups. We will then calculate simple correlations between these change scores and the pre-test values separately for quadriceps function, proprioception, and the KOOS. We hypothesize that individuals with greater quadriceps dysfunction and proprioceptive deficits combined with lower KOOS scores (i.e. greater pain, symptoms, etc.) will display greater improvements. Separately for each dependent variable, these variables will then be placed into a stepwise multiple regression model (starting with a forward selection step). In this way, the variable with the strongest relationship with the change score will be entered first, followed by the next strongest (after adjusting for the first), etc. The model selection will stop when no additional variables are identified to enter to leave the model at the 0.10 significance level. This less conservative significance level is selected to cast a wide net to include relevant candidate terms. Next, we will examine each of these terms, one-at-a-time, as an independent variable in another regression model where the change score is the dependent variable; an indicator term for the intervention (WBV vs. LMV) will also be included as an explanatory variable, as well as the interaction between the intervention indicator and the candidate term. The initial focus will be on the significance of the interaction term, as this will determine whether the effect of the candidate term is homogeneous (reflected by non-significance of the interaction at the 0.05 level) across the interventions, or not. If the test is non-significant, the interaction term will be removed and the model refitted; the candidate term is then assessed from this model regarding its ability to predict the homogeneous effect of LMV and WBV on the corresponding dependent variable. If the interaction test is instead statistically significant, then the interaction term is retained in the model, and statistical contrasts will be constructed to estimate and test the separate effects of the candidate term by intervention group.

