## **8 STUDY INTERVENTION ADMINISTRATION(if applicable)**

This preclinical investigation will utilize a single-blind randomized controlled experimental design whereby 75 individuals with primary unilateral ACLR will be randomly assigned to WBV, LMV, and Control groups. Stratified randomization into 3 groups of equal size (n = 25) will be performed using a computer generated randomization algorithm to ensure stratification with respect to age and time since ACLR. All individuals involved with data collection and analysis will be blinded to group allocation.

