## **9 SAFETY MANAGEMENT**

### **Research Monitor Responsibilities and Authorities**

[name] from the UNC-Chapel Hill Department of Orthopaedics will serve as the Research Monitor for this investigation. [name] possesses both the research ethics and medical expertise necessary to carry out this role. The PI will provide the Research Monitor a summary report during each quarter of the funding period that details information necessary for him to perform the following responsibilities:

1. Enrollment data
  - a. # of subjects (total and per group)
    - i. The Research Monitor will be unblinded to group, but the PI and all research team members involved with data collection will remain blinded.
    - ii. Groups will be identified by number only (e.g. Group 1 = Control, etc.) in reports generated by the PI, and the Research Monitor will be provided a key to decode group membership by the unblinded research assistants who are delivering the interventions.
    - iii. The Research Monitor will evaluate enrollment data to ensure the enrollment rate is consistent with the project timeline (i.e. 30 subjects per year for Years 1 and 2; 15 for Year 3).
  - b. The Research Monitor will verify subjects meet the enrollment criteria
    - i. Relevant data regarding the inclusion/exclusion criteria (e.g. age, KOOS scores, CAR, time since ACL reconstruction surgery, etc.) will be entered in an electronic data management system (Epi Info, Centers of Disease Control and Prevention). This system is capable of generating spreadsheets for data organization. These spreadsheets will be provided to the Research Monitor to permit verification of the enrollment criteria.
2. Verify consent
  - a. Data entry in Epi Info will require the member of the research team who is entering a given subject's data to verify (yes/no) that written informed consent was obtained. This individual will also be required to enter his/her initials in Epi Info to confirm that consent was obtained. The Research Monitor will verify that each subject has been consented based on these data contained in the quarterly report.

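### The Aim 1 and 2 ANCOVA leaves out the two factors used to stratify randomisation and adds covariates by an undefined imbalance rule, which costs precision if age or time since ACLR predicts the change score

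*Combined protocol and SAP*

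**What the plan says.** - **Randomisation.** The Synopsis, section 3.2 and section 8 all describe stratified allocation to three groups of 25. Section 3.2 says of the computer algorithm: "This algorithm will ensure stratification with respect to age and time since ACLR". Cut-points, number of strata and block size are not given.
- **Aim 1 model (section 6.2).** This is a one-way ANCOVA on pre-post change, with Dunnett comparisons against Control at two-sided 0.05 overall. One covariate is fixed: "The corresponding pre-test values for each dependent variable will be managed as a covariate in these models to increase precision of the treatment effects". Any others follow a rule: "Other covariates would include variables with random imbalances across the groups measured at the pre-test".
- **Aim 2 model (section 6.2).** "Aim 2 will be evaluated using the statistical models described above for Aim 1", with the WBV versus LMV contrast tested at two-sided 0.05.
- **Synopsis.** "Pre-Post change scores for each of the primary outcomes will be compared between groups via one-way ANCOVA". No covariate is named there.
- **Power (section 6.3).** The overall effect sizes use the pre-test score as the only covariate.
- **Blinding (section 8).** "All individuals involved with data collection and analysis will be blinded to group allocation".

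No section places age or time since ACLR in the Aim 1 or Aim 2 model.

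**The concern.** Stratifying makes the groups alike on age and time since ACLR, so the treatment estimate varies less from trial to trial if those factors affect the outcome. A model that omits them leaves their variance in the error term. The reported standard error then does not reflect the gain, confidence intervals are too wide, and the test is conservative.

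The imbalance rule does not repair this. It looks for chance differences between groups, and these two variables are the ones the design prevents from differing. It also selects on imbalance, where relation to outcome is what determines precision. With no candidate list, test, threshold or maximum number, the covariate set is settled only after baseline data are seen, and it can differ between outcomes because each has its own model.

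At stake are power and interval width for the Aim 1 and 2 comparisons, and a primary model that is not fully specified in advance.

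**Working it through.** **1. The plan's own figures.** Section 6.3 uses one-tailed tests, alpha 0.05 and power 0.80. The normal approximation is n per group = 2(1.645 + 0.842)²/d² = 12.37/d².
- d = 0.98 gives 12.9, so 13. d = 0.70 gives 25.2, so 26. This is the stated range of 13 to 26.
- d = 0.36 gives 97 by the exact t calculation, as stated.
- The overall F test gives 45 for f = 0.48, and 61 (63 in equal groups) for f = 0.41, as stated.

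The sample size is not in dispute here.

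**2. Inputs for the check.**
- From the documents: 25 per group; pre-test value in every model; Dunnett two-sided 0.05; effects against Control of 0.70, 0.78, 0.84 and 0.98; LMV versus WBV effect for CAR of 0.36.
- Assumed: R², the share of change-score variance left after pre-test adjustment that age and time since ACLR explain (0, 5, 10, 20%); two levels per factor; permuted blocks of 3 within the four strata; d in units of the SD after pre-test adjustment; no dropout.

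**3. Degrees of freedom.** Without the factors: 75 − 3 − 1 = 71. With one term each: 69. The Dunnett critical value moves from 2.257 to 2.258.

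**4. Formulas.** Under stratified allocation the true SD of the estimate is close to √(1 − R²) times its value at R² = 0, whether or not the factors are modelled. The reported SE shrinks only if they are.
- SE overstatement when omitted: 1/√(1 − R²) = 1.000, 1.026, 1.054, 1.118.
- Noncentrality when included: d√(25/2)/√(1 − R²). For d = 0.70 the numerator is 0.70 × 3.536 = 2.475. Dividing by 1, 0.975, 0.949 and 0.894 gives 2.475, 2.54, 2.61 and 2.77.

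**5. Simulation (20,000 trials per setting).** Power is for one Dunnett comparison, factors omitted → included.

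| Assumed R² | 0 | 5% | 10% | 20% |
|---|---|---|---|---|
| Reported SE / true SD, omitted | 1.002 | 1.027 | 1.054 | 1.116 |
| Reported SE / true SD, included | 1.002 | 1.002 | 1.002 | 1.002 |
| Familywise error, omitted | 0.049 | 0.043 | 0.037 | 0.026 |
| Familywise error, included | 0.049 | 0.049 | 0.049 | 0.049 |
| Power, d = 0.70 | 0.58 → 0.58 | 0.58 → 0.60 | 0.58 → 0.63 | 0.59 → 0.69 |
| Power, d = 0.98 | 0.88 → 0.88 | 0.88 → 0.89 | 0.89 → 0.91 | 0.90 → 0.94 |

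At R² = 5 / 10 / 20%, for the other effects:
- d = 0.78: 0.691 → 0.710, 0.695 → 0.737, 0.705 → 0.790.
- d = 0.84: 0.764 → 0.779, 0.770 → 0.803, 0.780 → 0.849.
- Aim 2, d = 0.36: 0.228 → 0.246, 0.221 → 0.256, 0.207 → 0.281.

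The noncentral-t calculation agrees to within about 0.01. For d = 0.70 with the factors included it gives 0.587, 0.612, 0.638 and 0.694. Blocks of 6, or 70/30 cuts, change the SE overstatement only to 2–3%, 5% and 10–12%.

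**6. Would the imbalance rule select the factors?** Without stratification, at least one of the two would be flagged in 1 − 0.95² = 10% of trials at p < 0.05 and 1 − 0.80² = 36% at p < 0.20. With stratification the simulated figures are 0.01–0.2% and 0.5–4%.

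**7. Does the missing threshold matter?** With eight independent unstratified candidates (assumed), the model changes in 1 − (1 − p)⁸ of trials: 34, 57 and 83% for thresholds 0.05, 0.10 and 0.20. Simulated familywise error under mechanical use is 0.038 to 0.051, so it is not inflated.

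**The case against.** - **The loss may be zero.** This stands. R² is unknown. The outcome is an immediate same-session change already adjusted for pre-test, and eligibility confines age to 18–35 and time since ACLR to 6 months to 5 years. Aim 3's candidate predictors are other variables: "We will then calculate simple correlations between these change scores and the pre-test values separately for quadriceps function, proprioception, and the KOOS". The loss of 0.10 needs both R² = 20% and the smallest effect; at 5% it is 0.01 to 0.02.
- **The scale of d is uncertain.** This also stands. Section 6.3 divides the pairwise differences by a pooled SD and mentions the pre-test covariate only for the overall f. If the tabulated values are unadjusted and pre-test explains 20–30% of change variance (assumed), the gain at R² = 10% falls from about 3.5 points to 1.8–2.4 at d = 0.84, and from 2.0 to 0.6–1.1 at d = 0.98. At d = 0.70 it falls less, from 4.6 points to between 3.5 and 4.0.
- **Power of 0.58 at d = 0.70 is not caused by this omission.** Correct. It appears at R² = 0 with or without the factors, because planning was one-tailed and the analysis is two-sided Dunnett.
- **The imbalance rule has no demonstrated inferential harm.** Largely correct. It acts on pre-test data, analysts are said to be blinded, and mechanical use does not inflate error. Eight independent candidates is only an illustration: peak torque, rate of torque development and CAR come from the same contractions. What remains is that the model is not defined in advance.
- **The randomisation algorithm is unspecified.** True, so the exact selection rates are assumed. Any algorithm that achieves the stated stratification would tend to balance these two variables.

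These points bear on the size of the gain. None shows a benefit from leaving the factors out.

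**Conclusion.** The concern holds. The Aim 1 and 2 model omits both stratification factors, and the imbalance rule is undefined and very unlikely to bring them in. This is lost precision. The estimates remain unbiased, and familywise error is at or below 0.05.

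Over an assumed R² of 0 to 20%, the standard error is overstated by 0 to 12%. Power lost per Aim 1 comparison is 0 to 0.10 at d = 0.70 and 0 to 0.04 at d = 0.98. The balance of cost and gain is one-sided: at R² = 0 adding both factors moves power at d = 0.70 only from 0.588 to 0.587. The change is worth making, though not essential to validity. Confidence in its size is moderate, because R², the strata, the block size and the scale of d are all assumptions.

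**What to change.** In section 6.2, fix the Aim 1 and 2 ANCOVA covariates as the outcome's pre-test value, age and time since ACLR. State one form for the last two (the randomisation categories or continuous values) and use it for every outcome. Simulation shows a similar gain from either form. Delete the imbalance rule, or keep it as a labelled sensitivity analysis with the candidate variables and threshold listed in advance. Align the one-line description in the Synopsis.

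The cost is about one sentence and two error degrees of freedom (71 to 69) if each factor enters as a single term, and more if a factor has several levels. N stays at 75. No new data are needed, since section 9 already has these items recorded: "e.g. age, KOOS scores, CAR, time since ACL reconstruction surgery, etc.) will be entered in an electronic data management system".

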3. **Treatment modalities that improve proprioception may reduce impulsive loading.** We evaluated the effects of stochastic resonance electrical stimulation (SR) on proprioception and gait biomechanics in individuals with knee OA (n=52). Impulsive loading was quantified from the loading rates of the peak vertical ground reaction force (vGRF) and heel strike transient (HST). The HST is a rapid, transient rise in the vGRF which occurs shortly following ground contact during gait that is indicative of impulsive loading. SR improved proprioception and altered gait biomechanics in manners that may slow knee OA progression. Specifically, SR increased the knee flexion angle at ground contact, decreased quadriceps/hamstring coactivation, and decreased impulsive loading (Figure 4). *These findings demonstrate that modalities that improve proprioception potentially reduce impulsive loading.* We anticipate that WBV and LMV will both improve proprioception in individuals who have undergone ACLR, thus altering gait biomechanics in manners that would reduce the risk of developing knee OA.

**Figure 4:** SR improved knee proprioception and reduced impulsive loading as evidenced by significant\*decreases in the loading rates (Body Weight/s) of the heel strike transient (HST) and peak vertical ground reaction force (vGRF) compared to the Control/no SR condition.

[figure not shown]

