#### **4.1 Screening/Baseline Visit procedures**

##### **Gait Biomechanics Assessment**

Subjects will walk forward along a 6m (~20 ft) walkway at a comfortable, self-selected “fast” speed while biomechanical data are collected. At least 5 practice trials will be performed during the familiarization session (Session 1) to determine the average preferred speed and ensure subjects can consistently strike a force plate mounted in the walkway with the test limb without noticeably altering their gait (i.e. “aiming” for the force plate). Gait speed will be monitored via an infrared timing system to ensure each trial is within  $\pm 10\%$  of the preferred speed. Kinematics (knee motion patterns), kinetics (knee joint moments and ground reaction forces) and lower extremity muscle activity (quadriceps and hamstrings EMG) will be sampled during each trial. Subjects will perform 5 valid trials from which gait biomechanical variables will be averaged for statistical analysis.

EMG electrodes will be placed over the back (hamstrings muscles) and front (quadriceps muscles) of the thigh via adhesive interfaces. Electrode placement sites will be shaved, lightly abraded, and cleansed with isopropyl alcohol to improve adhesion to the skin and signal quality. Motion capture markers will be secured on the trunk and pelvis, and the thigh, shank, and foot segments via double-sided tape. All measurement hardware will be further secured via hypoallergenic tape.

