### **6.3 Sample Size and Power**

Quadriceps function is the primary outcome for this investigation, as it is the critical factor in controlling impulsive knee joint loading linked to development of post-traumatic knee OA. We conducted *a priori* power analyses using data from our preliminary investigation involving these same vibratory stimuli following experimental knee joint effusion. Pre-post change scores were calculated as described above in the statistical methods for Specific Aim 1, and effect size indices were calculated for one-way ANCOVA using pre-test scores as the covariate. These analyses indicate that a sample of 45-63 subjects (15-21 per group) would provide statistical power of 0.80 for  $\alpha = 0.05$  to identify significant overall ANCOVA models for CAR ( $f = 0.48$ ) and peak torque ( $f = 0.41$ ), where  $f$  is the effect size calculated as the square root of the ratio of the between-group sum of squares and the error sum of squares. Further, these preliminary data generated the pairwise effect sizes presented in the table below calculated using the following equation:

$$\text{Effect Size} = \frac{[\Delta\text{WBV} \text{ (or } \Delta\text{LMV} \text{ )} - \Delta\text{Control}]}{\text{Pooled Standard Deviation}}$$

Effect Sizes for *Post Hoc* Group Comparisons of Pre-Post Change Scores

Quadriceps Function Variable	WBV vs. Control	LMV vs. Control	LMV vs. WBV
CAR	0.84	0.78	0.36
Peak Torque	0.98	0.70	0.35

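### Section 6.2 gives no rule for turning five gait trials into one heelstrike-transient (HST) yes/no per person, and within-arm McNemar tests use those trials inefficiently

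*Combined protocol and SAP*

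**What the plan says.** Section 6.2, under Specific Aim 1, gives HST its own test: "The number of individuals who display HST prior to and following the intervention (or control) will be compared via McNemar's test". The next sentence explains that the comparison is of "the proportion with HST at pre-test vs. post-test, separately for each group". So the data for each arm are 25 pairs of yes/no values, and no test compares the arms.

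Section 1.4 describes the feature: "The HST is a rapid, transient rise in the vGRF which occurs shortly following ground contact during gait that is indicative of impulsive loading". It gives no detection threshold. Section 4.1 (Gait Biomechanics Assessment) sets the number of walks and a general rule for combining them: "Subjects will perform 5 valid trials from which gait biomechanical variables will be averaged for statistical analysis". That sentence does not name HST.

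Three other places show how much weight the HST count carries:

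- The Synopsis lists the gait efficacy measures as "Gait biomechanics (vertical ground reaction force linear and instantaneous loading rates, peak internal knee extension moment, peak internal knee valgus moment". HST presence is not among them.
- Section 6.2 handles the change-score outcomes differently: "Mean change scores will be compared across groups (WBV, LMV, and Control) via one-way analysis of covariance (ANCOVA". Each model has the pre-test value as covariate, and Dunnett's procedure compares each vibration arm with Control.
- Section 6.3 says: "Quadriceps function is the primary outcome for this investigation".

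Section 4 has gait assessed before and after the intervention in Session 2. It describes Session 3 as the same apart from an added sensory assessment. No section says which session supplies the HST score.

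**The concern.** A transient after ground contact belongs to one footfall. Five walks can therefore give a person anything from 0 to 5 trials with HST, and the McNemar test needs that reduced to one yes/no. The plan gives no rule for a person with 1 to 4. An any-trial, a majority and an all-five rule can give very different head counts from the same recordings, and the choice is still open once the data are in.

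Whichever cut is chosen, reducing five trials to one yes/no drops information. A person who goes from five trials with HST to one is scored as unchanged under an any-trial rule.

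Testing each arm separately adds to this. A significant fall in a vibration arm is not a comparison with Control, although the design and the ANCOVA supply one for the other gait measures. HST is one of the plan's markers of impulsive loading, so its result is likely to be read as evidence on mechanism.

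**Working it through.** **Inputs from the documents.** Five valid trials per assessment (4.1); 25 subjects per arm (3.2, 6.3); two-sided 0.05 (6.2). **Assumed, because the documents give no HST figure:** the HST rate per trial, its spread between people, and the size and form of the effect.

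**Step 1: the plan's own figures.** There is none for HST. The nearest is 13 to 26 per group for vibration versus Control on quadriceps function (6.3, one-tailed 0.05, power 0.80). With n = 2(1.645 + 0.842)²/d² = 12.37/d²:

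- d = 0.98 gives 12.37/0.960 = 12.9, so 13.
- d = 0.70 gives 12.37/0.49 = 25.2, so 26.

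The range reproduces, and it does not bear on HST.

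**Step 2: the effect of the cut when all subjects are alike.** Suppose each trial shows HST independently with probability 0.3.

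- Any trial: 1 − 0.7⁵ = 1 − 0.168 = 0.83.
- At least three: 10(0.3³)(0.7²) + 5(0.3⁴)(0.7) + 0.3⁵ = 0.132 + 0.028 + 0.002 = 0.16.
- All five: 0.3⁵ = 0.002.
- Mixed (1 to 4 trials): 1 − 0.168 − 0.002 = 0.83.

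**Step 3: subjects who differ.** Let subject i have log-odds of HST θᵢ ~ N(μ, SD²), with the pre-test count ~ Bin(5, expit θᵢ). At μ = 0 and SD 2, about 61% of subjects are mixed at pre-test. Over μ from −1 to 1 and SD from 1 to 6, the mixed share runs from 26% to 81%.

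**Step 4: power under a uniform effect.** Vibration lowers every treated subject's log-odds by 1, so the post-test count ~ Bin(5, expit(θᵢ − 1)). Controls do not change. Within an arm, McNemar's statistic is (b − c)²/(b + c), where b and c count those who lose and gain HST. Between arms, change is regressed on arm and pre-test score, with 25 per arm and no Dunnett adjustment. Simulated results at μ = 0, SD 2:

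| Score | Pre-test prevalence | Within one arm | One vibration arm vs Control |
|---|---|---|---|
| Any trial | about 81% | 0.29 (McNemar) | 0.22 |
| At least 3 of 5 | about 50% | 0.49 (McNemar) | 0.36 |
| All 5 | about 19% | 0.23 (McNemar) | 0.19 |
| Count or proportion of 5 | not applicable | 0.81 (paired t) | 0.62 |

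Repeat simulations differed by at most 0.03 within arm and 0.05 between arms. The two power columns answer different questions. The last column is the one relevant to the fix.

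**Step 5: the rest of the uniform-shift grid (μ −1 to 1).** For SD 1 to 3, between-arm power is 0.43 to 0.80 for the proportion. For the yes/no scores it runs from about 0.00 (all-five rule, HST rare) to 0.59. At SD 6 it is 0.24 to 0.25 for the proportion and 0.08 to 0.12 for the yes/no scores. The proportion was ahead in every cell. With no effect (μ = 0 and 1, SD 2), the paired test on the count rejects at 0.05, so its gain is not bought with a raised error rate.

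**Step 6: other forms of effect.** Suppose vibration abolishes HST in 30% of subjects (log-odds lowered by 8) and does nothing in the rest. Between-arm power is then about 0.50 for the any-trial score against 0.44 for the trial count at SD 2, and 0.63 against 0.42 at SD 1. With 40% responders the figures are 0.74 and 0.66. Separately, if the uniform model is given person-level pre-post drift of SD 1, power for the between-arm analysis of the proportion falls from 0.60 to 0.43.

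**The case against.** A reader might infer that 4.1 and 6.2 define HST in two conflicting ways, as a five-trial average and as a yes/no. The documents do not support that. The averaging sentence in 4.1 is general and does not name HST, while 6.2 names it and gives it a rule of its own. HST could also be read once per person from an averaged force curve, in which case nobody is mixed. What is left is an incomplete definition, because neither reading is stated.

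A reader might also infer that the trial loses much of its power. That does not follow. Impulsive loading is already analysed continuously through the vertical ground reaction force loading rates, which go into the three-arm ANCOVA. HST presence is not a listed efficacy measure, and the sample size rests on quadriceps function. Even for HST, the loss comes from an assumed model, and step 6 shows an all-or-nothing response in which an any-trial score does better than the count.

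Two further points carry some weight. Section 8 blinds those who collect and analyse data to allocation, which limits choosing a cut to suit a result but does not rule it out. A head count of people with a transient is also a legitimate and readable summary, but only once its rule is written down.

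**Conclusion.** The point holds as a missing per-person rule together with an inefficient analysis, and it is confined to the supplementary HST test. The missing rule is a matter of reading the documents and needs no model. It matters most if HST is read trial by trial.

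The size is illustrative. In the central case the unstated cut moves pre-test prevalence between about 19% and 81%. Scoring the proportion of trials raises power against Control from 0.19–0.36 to about 0.62, before Dunnett adjustment. These figures assume independent trials given the person, normally distributed log-odds and a uniform one-unit reduction. The advantage is common but not general: it can vanish or reverse against an any-trial score if vibration abolishes HST in a subset. If people differ very widely (SD 6), the proportion itself has power of only about 0.25. The stated sample size and the main gait analysis are unaffected.

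**What to change.** In section 6.2:

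1. Define HST on a single trial, including how it is detected, and state which session supplies it.
2. Make the outcome the proportion of the five valid trials that show HST at each assessment.
3. Analyse its pre-post change with the ANCOVA and Dunnett procedure already planned for the other gait variables, with the pre-test proportion as covariate. This also gives HST a direct comparison with Control.
4. Add a binomial mixed model on the trial-level yes/no data as a sensitivity analysis.
5. Keep any head count of individuals, and McNemar's test within arms, as descriptive, with one cut fixed in advance (for example, at least three of five trials).

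The change is to the wording of the analysis plan. It needs no new subjects, visits or recordings. If the intention was to read HST from an averaged curve, reading each of the five recorded trials is some extra processing. The statistical downside is small: a 0-to-5 score is bounded and not normal, which the sensitivity model addresses, and it is slightly less simple to report than a head count.
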